### **Remote Visits Due to the COVID-19 or any Pandemic**

If visits cannot be conducted onsite due to travel restrictions or other pandemic-related reasons, phone or virtual (remote) visits, or visits at alternative locations may be performed. These visits should occur within 7 days of the planned date, if possible. During these visits, the following procedures should be performed:

- Adverse event assessment

- Concomitant medications
- Compliance to contraception (if applicable)
- Monthly pregnancy testing results (if applicable)
- IP compliance/dosing and drug accountability
- Confirm subject diary entries
- Weight (may be performed by the subject or caregiver)
- Vital signs (may be obtained by the subject or caregiver)
- Questionnaires: All questionnaires except EQ-5D-5L scale are eligible for completion by remote interview at all visits. If there are time constraints to the remote visit, at a minimum, the following must be completed: IBDQ, FACIT-F, PGIC, PGIS.

Assessments that require physical examination (e.g., gentle compression of fistulas, etc.) should not be performed.

The site must keep records of all remote visits.

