- # Study activity that can be performed by phone/virtually within a  $\pm$  7-day window when an onsite study visit is not possible due to COVID-19 or any pandemic, if allowed by local regulations. This is applicable for all visits, except Screening and Baseline visits, which must be completed at the study site. Physical examination that requires palpation should not be performed. Patient questionnaire EQ-5D-5L is not eligible to be performed by phone/virtually.
- + Study activity that can be performed at a local facility when an onsite study visit is not possible due to COVID-19 or any pandemic, if allowed by local regulations. This is applicable for all visits, except Screening and Baseline visits, which must be completed at the study site.
- = Study activity should not be performed by phone/virtually or at a local facility, when an onsite study visit is not possible due to COVID-19 or any pandemic. Screening and Baseline visit procedures must be completed at the study site.

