 - Markov Chain Monte Carlo (MCMC) will be first applied to augment data into monotonic missing pattern (where applicable) and PROC MI will be used to generate 30 datasets using the regression method. If the binary endpoints are derived from the continuous variables, PROC MI will be applied to the continuous variables. The variables to be included in the imputation model are: treatment group, randomization stratification factors (baseline steroid use (Yes, No), endoscopic disease severity (SES-CD < 15, ≥ 15) and number of prior biologics with inadequate response or intolerance (≤1, > 1)), age, gender, weight, baseline measurement (if applicable) and post-baseline measurements at each visit up to the end of the analysis period. The random seed for MCMC and the random seed for PROC MI are specified in [Appendix I](#). The imputed post-baseline measurements will be rounded to the same precision as the observed data before the determination of responder status. Subjects will be characterized as responders or non-responders based on MI imputed data. Using the CMH model adjusted by randomization stratification factors, the endpoints will be analyzed using each of the 30 imputed datasets. SAS PROC MIANALYZE will be used to generate the final inferences of the risk difference between upadacitinib group and placebo group, using Rubin's rule³. Note that measurements will be set to missing for 1) at or after the occurrence of the CD-related corticosteroids intercurrent event 2) on/after the date of initiation of CD-related confounding medications after premature discontinuation of study drug

before applying MI. After the MI imputation, an NRI override will be implemented for missing values 1) missing values due to reasons other than COVID-19 infection or logistic reasons, or 2) at or after the occurrence of the CD-related corticosteroids intercurrent event or 3) on/after the date of initiation of CD-related confounding medications after premature discontinuation of study drug, that is, regardless of MI imputed values, subjects satisfying 1) or 2) or 3) will be considered as "non-responder" for binary efficacy endpoints.

For binary efficacy endpoints regarding the occurrence of hospitalization and the occurrence of CD-related surgeries, missing data will be handled using the following approaches.

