 - d. The "14-4 approach" will be used to calculated CDAI, average daily SF/AP at each CDAI date. Sensitivity analyses which are based on "9-2 approach" to calculate CDAI and SF/AP will be performed on primary endpoints (Clinical Remission per CDAI at Week 12, Clinical Remission per PROs at Week 12).
3. Subtotal scores for components 4-6 (Number of 6 listed categories, usage of Lomotil/Imodium/Loperamide/opiates for diarrhea and abdominal mass) will be determined using the data collected on the CDAI calculation date and the corresponding formula in the table above;
4. Subtotal score for component 7 (Hematocrit) is calculated as follows:
- a. Identify the Hematocrit (%) value form the same visit as the CDAI calculation date, use the Hematocrit that is closest to the CDAI calculation date;
 - b. Hematocrit values obtained from previous visits can be used.
 - c. The subtotal score for Hematocrit is calculated using the formula in the table above. If Hematocrit value is greater or equal to 47% for male subjects (greater or equal to 42% for female subjects), the subtotal score is set to 0.

5. Subtotal score for component 8 (percentage below standard weight) is calculated as follows:
 - a. Standard weight is calculated based on height obtained at screening, sex and study protocol Appendix H;
 - b. Body weight is based on the measurement obtained on the CDAI calculation data, or previous visits if the measurement is missing.
 - c. The subtotal score for percentage below standard weight is calculated using the formula in the table above.
6. CDAI score is calculated as the sum of subtotal scores of 8 components, and the total CDAI score will be rounded to 1 decimal. If any of the subtotal scores are missing, the CDAI score will be missing.

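### A Week 12 CDAI left incomplete by COVID-19 is imputed as a single total, which discards the same-visit diary and allows imputed scores that contradict it

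*SAP*

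**What the plan says.** **Scoring (SAP Appendix D).** The CDAI is the sum of eight weighted subtotals. Items 1-3 come from the home diary. For items 4-6 the subtotals "will be determined using the data collected on the CDAI calculation date", with no fallback. Items 7 and 8 have one: "Hematocrit values obtained from previous visits can be used", and "Body weight is based on the measurement obtained on the CDAI calculation data, or previous visits if the measurement is missing". Rule 6 then states: "If any of the subtotal scores are missing, the CDAI score will be missing".

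**Missing data (SAP 9.2.1 and Appendix I).** The primary approach, NRI-C, uses multiple imputation for data missing because of COVID-19 and non-response otherwise. "If the binary endpoints are derived from the continuous variables, PROC MI will be applied to the continuous variables". The listed predictors are treatment, the three stratification factors, age, gender, weight, and the baseline and post-baseline measurements. Table I-1 gives CDAI one row but lists SES-CD as 20 individual variables. Well-being has no row.

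**Pandemic visits (Protocol).** In Appendix C the CDAI row carries the equals mark, defined as: "Study activity should not be performed by phone/virtually or at a local facility, when an onsite study visit is not possible due to COVID-19". The list of remote-visit tasks in 5.3.1.1 includes "Confirm subject diary entries", weight taken by the subject or a caregiver, and concomitant medication review. It rules out assessments that need a physical examination.

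**The concern.** For a subject seen remotely at Week 12, the items that carry much of the score are on file and the examination items are not. The plan treats this subject like one about whom nothing is known at Week 12. The imputed total can then fall below what the observed items alone add up to.

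The same diary is used directly to derive clinical remission per PROs. One subject can therefore be an observed non-remitter on PROs and an imputed remitter on CDAI, although the diary excludes the second result. Clinical remission per CDAI at Week 12 is a US co-primary endpoint and the first EU ranked secondary.

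**Working it through.** **1. The plan's own figure.** Protocol 8.2 and SAP 2.4 claim at least 95% power for CDAI remission of 20% against 40%, with 165 and 330 subjects, Fisher's exact test and two-sided 0.05. Exact enumeration gives 99.6%. The claim reproduces.

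**2. What is available at a remote visit.**

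| Item | Status |
|---|---|
| 1-3 stools, pain, well-being | Observed, from the diary |
| 4 manifestations, fistula, fever | Usually incomplete without an examination; no fallback |
| 5 anti-diarrheals | Uncertain. Protocol 5.1 has it recorded daily, but the diary contents in 10.3 and Appendix C footnote w omit it. Concomitant medication review may recover it |
| 6 abdominal mass | Usually missing; no fallback |
| 7 hematocrit | May be carried forward (SAP rule 4b) |
| 8 weight | Observed, or carried forward (SAP rule 5b) |

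This takes the remote visit date as the CDAI calculation date, which the SAP does not say expressly.

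**3. What the diary alone settles.** From the Appendix D weights, with daily averages SF (stools), AP (pain) and WB (well-being):

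diary subtotal = 7 x (2 x SF + 5 x AP + 7 x WB)

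- SF 4, AP 2, WB 1: 7 x (8 + 10 + 7) = 175.
- SF 4, AP 2, WB 2: 7 x (8 + 10 + 14) = 224.
- SF 2.8, AP 1, WB 1: 7 x (5.6 + 5 + 7) = 123.2.

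No subtotal is negative, because items 7 and 8 are set to 0 when hematocrit or weight is above the reference. The first two subjects are therefore non-remitters whatever the other items are. The third is not settled: item 4 can add 0 to 120 (6 x 20) and item 6 can add 0 to 50 (5 x 10).

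How often non-remission is settled depends on item distributions that the documents do not give. I assumed means before truncation of SF 2.8, AP 1.1 and WB 1.1, with SDs of 1.5-2.5, 0.6-0.9 and 0.6-1.0 and correlations of 0.4-0.6. In that simulation the diary reached 150 in 37.1%, 40.8% and 42.6% of subjects, and non-remission was 71.1%, 67.0% and 64.1%. The diary alone thus settles 37.1/71.1 = 52% to 42.6/64.1 = 66% of non-remitters. Adding items 5, 7 and 8, all taken as known without error, raises this to 87-89%.

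**4. Individual draws (illustrative only).** Let R2 be the share of Week 12 CDAI variance that the predictors explain, p the remission rate and t its normal quantile. A draw falls on the wrong side of 150 with probability 2 x [p - Phi2(t, t; R2)], where Phi2 is the bivariate normal distribution function.

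| Assumed R2 | p = 20% | p = 40% |
|---|---|---|
| 0.36 (other-visit totals, weak) | 26% | 37% |
| 0.64 (other-visit totals, strong) | 19% | 27% |
| 0.80 (diary, within its simulated 75-89%) | 14% | 20% |
| 0.90 to 0.95 (six items, simulated 91-96%) | 10% to 7% | 14% to 10% |

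**5. Trial level.** Let f be the share of Week 12 scores missing because of COVID-19. The unexplained share is w = [p - Phi2] / [p(1 - p)], and each arm's variance is inflated by 1/(1 - f x w). For f = 15% and R2 = 0.36:

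- w = 0.128/0.16 = 0.80 (placebo) and 0.1845/0.24 = 0.77 (upadacitinib).
- Inflation = 1/(1 - 0.12) = 1.136 and 1/(1 - 0.115) = 1.130.
- SE = sqrt(0.16/165 x 1.136 + 0.24/330 x 1.130) = 0.0439, against 0.0412 with nothing missing.

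| f | Power, R2 0.36 to 0.64 | Power, R2 0.90 |
|---|---|---|
| 5% | 99.56% to 99.59% | 99.63% |
| 15% | 99.23% to 99.38% | 99.54% |

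**The case against.** Refusing to score an index with missing components is conventional. Multiple imputation aims at the arm-level rates, not at each subject. With 30 imputations and Rubin's rules, draws that are wrong for individuals can still give a correct risk difference under the missing-at-random assumption in SAP 9.2. NRI-NC and the tipping-point analysis already test whether the conclusion depends on the imputation. **This stands**, and it is why the percentages in step 4 must not be read as error rates of the trial. But NRI-NC, tipping point, as-observed and the 9-2 diary analysis all keep rule 6, so none of them recovers the discarded items.

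The remote score is also less complete than it may look. Item 5 is not clearly a diary item. A carried-forward hematocrit is not an observation, and Protocol 5.3.1.1 requires the same-visit value, allowing the preceding one only for technical loss. **This stands too:** what is securely observed is the diary and weight.

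In the other direction, examinations can take place at home healthcare visits or, by the plus mark on the examination row of Appendix C, at a local facility. Not every off-site visit lacks items 4 and 6.

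Finally, items 4 and 6 are discrete (a count of 0 to 6; a score of 0, 2 or 5) and do not suit the normal-theory method in 9.2.1. That is a real programming cost, but a modest one.

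**Conclusion.** The point holds as an inexpensive improvement. Total-level imputation under rule 6 discards same-visit data in a US co-primary endpoint and permits imputed remissions that the observed items exclude. This follows from the scoring weights and the listed predictors, without further assumptions.

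A reader might infer that the US co-primary is biased, that its power is at risk, or that a nearly complete score is thrown away. The documents do not support these readings. No bias is shown under missing at random. The power loss is under one point at up to 15% affected visits, from a starting point of 99.6%. The score is partly complete: four items are normally observed, two may be recoverable and two are usually absent.

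The size figures rest on assumed R2 values, item distributions and missing shares. The documents give neither the number of affected Week 12 visits nor the correlation of CDAI between visits. SAP 9.2 says that impacted visits are recorded, so the sponsor can count them.

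**What to change.** In SAP 9.2.1, Appendix D and Appendix I, for a CDAI that is incomplete because of COVID-19:

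- Keep the observed same-visit subtotals and impute only the missing ones, with the observed subtotals and earlier item values as predictors. Then sum and apply the cut-off of 150. This follows the component-level approach already used for SES-CD.
- Keep the non-responder overrides for other missingness, corticosteroid events and confounding medication.
- State which date is the calculation date at a remote visit and where item 5 comes from. Align SAP rule 4b on hematocrit with Protocol 5.3.1.1.
- At minimum, add the same-visit diary subtotals as predictors in the CDAI imputation model, and do not let an imputed total fall below the sum of the observed subtotals.

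No new data are needed. The cost is SAP wording, a somewhat longer imputation program, and a suitable model for the discrete items 4 and 6.

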Appendix E. Simple Endoscopic Score – CD (SES-CD)

SES-CD is calculated based the sum of individual segment values for four endoscopic variables (presence and size of ulcers, ulcerated surface, affected surface and presence of narrowing). Each variable in each segment be scored 0 to 3 resulting in SES-CD values ranging from 0 to 56 with higher scores indicating more severe disease.

Variable	Score			
	0	1	2	3
Size of ulcers (cm)	None	Aphthous ulcers (diameter 0.1–0.5)	Large ulcers (diameter 0.5–2)	Very large ulcers (diameter >2)
Ulcerated surface (%)	None	<10	10–30	>30
Affected surface (%)	Unaffected segment	<50	50–75	>75
Presence of narrowings	None	Single, can be passed	Multiple, can be passed	Cannot be passed

* Total SES-CD: sum of the values of the 4 variables for the 5 bowel segments. Values are given to each variable and for every examined bowel segment (for example, rectum, left colon, transverse colon, right colon and ileum).

Medscape Source: Nat Rev Gastroenterol Hepatol ©2009 Nature Publishing Group

[figure not shown]
SES-CD Scoring:

	Rectum	Sigmoid and Left Colon	Transverse Colon	Right Colon	Ileum	Total
Size of Ulcers Enter: 0 if none 1 if aphthous ulcers (Ø 0.1 to 0.5 cm) 2 if large ulcers (Ø 0.5 to 2 cm) 3 if very large ulcers (Ø > 2 cm)						
Ulcerated Surface Enter: 0 if none 1 if < 10% 2 if 10% – 30% 3 if > 30%						
Affected Surface Enter: 0 if unaffected segments 1 if < 50% 2 if 50% – 75% 3 if > 75%						
Presence of Narrowing Enter: 0 if none 1 if single, can be passed 2 if multiple, can be passed 3 if cannot be passed						
					TOTAL =	

Appendix F. Patient Reported Outcomes Questionnaires Descriptions

IBDQ – Inflammatory Bowel Disease Questionnaire

The IBDQ is a 32-item (ranges 1 – 7) self-report questionnaire for patients with IBD to evaluate the patient reported outcomes across 4 dimensions: bowel symptoms (loose stools, abdominal pain), systemic symptoms (fatigue, altered sleep pattern), social function (work attendance, need to cancel social events), and emotional function (anger, depression, irritability). The IBDQ total Score ranges from 32 to 224 with a higher score indicating better outcome.

The derivation of the IBDQ total score and the four IBDQ domain scores are as follows:

Domain Scores:

S1. BOWEL SYMPTOM: Q1 + Q5 + Q9 + Q13 + Q17 + Q20 + Q22 + Q24 +
 Q26 + Q29
 [score ranges from 10 - 70],

S2. SOCIAL FUNCTION: $Q4 + Q8 + Q12 + Q16 + Q28$

[score ranges from 5 - 35],

S3. SYSTEMIC SYMPTOM: $Q2 + Q6 + Q10 + Q14 + Q18$

[score ranges from 5 - 35],

S4. EMOTIONAL FUNCTION: $Q3 + Q7 + Q11 + Q15 + Q19 + Q21 + Q23 + Q25 + Q27 + Q30 + Q31 + Q32$

[score ranges from 12 - 84].

Total Score:

IBDQ Total Score = SUM of (bowel symptom domain score, social function domain score, systemic symptom domain score, emotional function domain score).

The following convention applies to IBDQ:

When not more than 20% of items in a domain of IBDQ were missing, it was substituted with the mean values from the items completed in the particular domain; otherwise, they were treated as missing. The 20% threshold in each domain is: bowel symptom domain: 2 items, systemic symptom domain: 1 item, social function domain: 1 item, emotional function domain: 2 items. If any of the 4 domain scores is missing, the total IBDQ score will be set to missing.

WPAI-CD – Work Productivity and Activity Impairment Questionnaire-Crohn's Disease

The WPAI assesses the impact of the condition on work productivity losses and impairment in daily activity. WPAI has six items covering four domains: Absenteeism (work time missed), measured as the number of hours missed from work in the past 7 days due to a condition related problem. Scores are expressed as impairment percentages, adjusting for hours actually worked according to the WPAI scoring algorithm; Presenteeism (impairment at work/reduced on-the-job effectiveness), measured as the impact of the condition on productivity while at work (i.e., reduced amount or kind of work, or not as focused as usual). Responses are recorded on a 0 – 10 Likert scale

(where, 0 = no effect of CD on work and 10 = severe impact of CD while at work); productivity loss (overall work impairment), measured as the sum of hours missed due to condition i.e., absenteeism and number of hours worked with impairment i.e., product of number of hours worked and presenteeism; and activity impairment (i.e., activities other than paid work like work around house, cleaning, shopping, traveling, studying), recorded and scored in same way as presenteeism. Higher numbers indicate greater impairment and less productivity.

CSS – Crohn's Symptoms Severity Questionnaire

The CSS questionnaire is a 14-item assessment of both GI and non-GI CD symptoms using a 7-day recall period. The 14 items assess the frequency or intensity of each individual symptom by utilizing a 5-point Likert-type scale. An assessment of an individual items frequency and intensity is measured as follows:

- Frequency: 1 = Never, 2 = Rarely, 3 = Sometimes; 4 = Often, 5 = Always
- Intensity: 1 = Not at all, 2 = A little bit; 3 = Somewhat; 4 = Quite a bit; 5 = Very much

An overall symptom score is calculated by combining ratings from the 14 individual items (possible scores range from 14 to 70) with higher scores indicating greater symptom frequency or intensity.

SF-36 – Short Form 36

The SF-36 questionnaire is a self-administered multi-domain scale with 36 items. Eight subscales cover a range of functioning: physical functioning, role-physical, bodily pain, general health, vitality, social functioning, role-emotional, and mental health. The scoring yields a physical component score, a mental component summary score, and subscale scores. Higher scores represent better outcomes. The concepts measured by the SF-36 are not specific to any age, disease, or treatment group, allowing comparison of relative burden of different diseases and the benefit of different treatments.

EQ-5D – European Quality of Life 5 Dimensions

The EQ-5D-5L is a standardized non-disease specific instrument for describing and valuing health-related quality of life. The EQ-5D consists of 5 dimensions: mobility, self-care, usual activity, pain/discomfort, and anxiety/depression. Each dimension has 5 levels: no problem, slight problem, moderate problem, severe problem or unable to do the activity. It also contains a Visual Analogue Scale (VAS). Subjects are asked to indicate the level that describes their current level of function or experience for each dimension. As a measure of health status, it provides a descriptive profile and can be used to generate a single index value for health status, where full health is equal to 1 and death is equal to 0. The VAS records the subject's assessment of his/her own health along a vertical 20 cm line, which has health state scores between 0 and 100.

FACIT-F – Functional Assessment of Chronic Illness Therapy-Fatigue

The Functional Assessment of Chronic Illness Therapy (FACIT) measurement system is a comprehensive compilation of questions that measure health related quality of life in patients with cancer and other chronic diseases (www.facit.org). The FACIT-F scale is a symptom-specific subscale of FACIT and is composed of 13 fatigue-related questions as follows. The response to each question is as follows: 0=Not at all, 1=A little bit, 2=Somewhat, 3=Quite a bit, 4=Very much.

1. I feel fatigued
2. I feel weak all over
3. I feel listless ("washed out")
4. I feel tired
5. I have trouble starting things because I am tired
6. I have trouble finishing things because I am tired
7. I have energy
8. I am able to do my usual activities

9. I need to sleep during the day
10. I am too tired to eat
11. I need help doing my usual activities
12. I am frustrated by being too tired to do the things I want to do
13. I have to limit my social activity because I am tired

In order to have higher values representing lower level of fatigue, all of the items, except for item 7 "I have energy" and item 8 "I am able to do my usual activities," are assigned reversed scores: reversed score = 4 – raw score. The total FACIT-F score will then be calculated as follows:

- $\text{FACIT-F score} = 13 \times [\text{Sum of answered-item scores} / \text{Number of items answered}]$

The score ranges from 0 to 52, 52 being the lowest level of fatigue.

When there are missing data, provided that more than 50% of the items (i.e., at least 7 of 13 items) were answered in FACIT-F questionnaire, the total score will not be deemed as missing but be calculated as the mean response for all the non-missing-value items. If less than 50% of the items were answered, the total score will have a missing value.

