### **FACIT-F – Functional Assessment of Chronic Illness Therapy-Fatigue**

The Functional Assessment of Chronic Illness Therapy system is a collection of quality of life (QoL) questionnaires targeted to the management of cancer and other chronic illnesses. The FACIT-F questionnaire was developed to assess fatigue associated with anemia. It consists of 13 fatigue-related questions. The responses to the 13 items on the FACIT-F questionnaire are each measured on a 4-point Likert scale. The responses to the answers are the following: (i) not at all: 0 points; (ii) a little bit: 1 point; (iii) somewhat: 2 points; (iv) quite a bit: 3 points; (v) very much: 4 points. Thus, the total score ranges from 0 to 52. High scores represent less fatigue.

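### The SAP's FACIT-F missing-item rule omits the factor of 13 in its own scoring formula; if programmed as written, it would mis-scale partly answered forms in a ranked secondary endpoint

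*SAP*

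**What the plan says.** SAP Appendix F (FACIT-F) lists 13 items with response codes "0=Not at all, 1=A little bit, 2=Somewhat, 3=Quite a bit, 4=Very much". All items except 7 and 8 "are assigned reversed scores: reversed score = 4 – raw score". The total is then 13 multiplied by a ratio whose numerator is "Sum of answered-item scores" and whose denominator is the number of items answered. The SAP adds: "The score ranges from 0 to 52, 52 being the lowest level of fatigue". Protocol Appendix E agrees: "Thus, the total score ranges from 0 to 52".

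A separate paragraph in SAP Appendix F deals with missing items. It applies once 7 or more of the 13 have a response, and its instruction for such a form is that "the total score will not be deemed as missing but be calculated as the mean response for all the non-missing-value items". Below that threshold the total is missing. No multiplication by 13 appears in this paragraph, and nothing says whether it replaces or restates the formula above it.

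SAP Section 3.2 places the Week 12 change in FACIT-F total score fifth in Group 1A_E (EU/EMA) and fourth in Group 1A_F (US/FDA). Under SAP Section 12.0, Group 1A is tested in fixed order, and Group 1B only if all of Group 1A is significant.

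**The concern.** The paragraph written specifically for incomplete forms defines a quantity on a different scale from the total score. A programmer who treats the specific rule as overriding the general formula would put a value of at most 4 into a 0 to 52 variable. A range check would not catch it, because 0 to 4 lies inside 0 to 52. It is also unclear whether the averaged response is the raw answer or the reversed item score.

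What is at stake is a gatekeeping endpoint. If FACIT-F is not significant, IBDQ (the next endpoint in both schemes) and all of Group 1B are not formally tested. The same score feeds three further Part 1 endpoints in SAP Section 3.3.1: gains of at least 7, 9 and 11 points at Week 12.

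**Working it through.** **Inputs.** 13 items, each scored 0 to 4; the scoring formula; the threshold of 7 items; the stated range of 0 to 52 (all SAP Appendix F; range also in Protocol Appendix E).

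**Step 1: reproduce the stated range.** Every answered item at 0 gives 13 x 0 = 0. Every answered item at 4 gives 13 x 4 = 52. This holds for any number of items answered, because the formula divides by that number. The 0 to 52 range reproduces exactly, and the formula already prorates.

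**Step 2: check the threshold.** 7/13 = 53.8%, above one half; 6/13 = 46.2%, below it. The cut-off is consistent.

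**Step 3: apply both rules to the same form (reversed item scores).**
- 12 items answered, each scored 3: formula 13 x 36/12 = 39.0; missing-item sentence 36/12 = 3.0.
- 7 items answered, summing to 18: formula 13 x 18/7 = 33.4; missing-item sentence 18/7 = 2.57.

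The ratio is 13 in both cases. It is not fixed if the sentence means raw answers. Take 12 answered items: ten reversed items with raw answer 1, and items 7 and 8 with raw answer 3. The raw mean is (10 + 6)/12 = 1.33, every scored item is 3, the formula gives 39, and 39/1.33 = 29.25.

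**Step 4: carry this to the endpoint, a change from baseline.** Take a subject whose formula scores are 26 at baseline and 36 at Week 12. The change by the formula is +10 in every row.

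| Partly answered form | Change if the missing-item sentence is applied literally |
|---|---|
| Neither | 36 - 26 = +10 |
| Week 12 only | 36/13 - 26 = 2.77 - 26 = -23.2 |
| Baseline only | 36 - 26/13 = 36 - 2 = +34 |
| Both | 2.77 - 2 = +0.77 |

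For the responder endpoints, a literal Week 12 score of at most 4 cannot show a gain of 7 or more against a complete baseline form.

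**Step 5: illustration of the effect on the test.** None of these inputs is in the documents. Assume SD 11, a Week 12 mean of 32, complete baselines, a share f of Week 12 forms partial in both arms, and 330 versus 165 subjects. A mis-scaled form shifts by about 32 x 12/13 = 29.5 points. The SD becomes sqrt(11² + f(1 - f) x 29.5²), and the true difference d becomes d(1 - f) + f x d/13.

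| f | SD | Power, d = 3 | Power, d = 4 | Power, d = 5 |
|---|---|---|---|---|
| 0% | 11.0 | 82% | 97% | 99.8% |
| 1% | 11.4 | 78% | 96% | 99.5% |
| 5% | 12.8 | 65% | 88% | 97.5% |
| 10% | 14.1 | 53% | 77% | 92% |

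This is a simple two-sample comparison, not the baseline-adjusted MMRM of SAP Section 9.2.2. It shows only how the effect would grow with f.

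**The case against.** The strongest reply is that the SAP already contains the right rule. The formula speaks of answered items and of the number answered, which matters only when items are missing, and it is not restricted to complete forms. On that reading the later paragraph merely adds the 7-item threshold and describes the same proration loosely. The rest of the text supports this: both documents fix the range at 0 to 52, and gains of 7, 9 or 11 points are impossible on a 0 to 4 scale. The IBDQ rule in the same appendix fills missing items with the domain mean, which keeps the scale.

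This stands as an argument about what was probably meant. It does not remove the conflict, because the sentence addressed to incomplete forms still says that the total is the mean.

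A reader might infer that the ranked endpoint will be corrupted, or that the error always appears as false worsening. The documents support neither. The first requires literal programming against the formula and the range. The second holds only when the Week 12 form alone is partial.

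It is also fair to object that partial forms may be rare. Protocol Section 10.3 has the questionnaire completed on an electronic tablet, with interview as a pandemic fallback, and nothing says whether items can be skipped. The effect could be nil.

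**Conclusion.** The missing-item sentence is wrong as written: it contradicts the formula and the stated range by a factor of 13 on reversed item scores. This is a wording error with a conditional consequence. Only if the sentence is programmed literally would the Week 12 change be falsely low (Week 12 form partial), falsely high (baseline form partial) or shrunk towards zero (both partial).

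The size for a single form is certain. The effect on the FACIT-F test, and so on the gate to IBDQ and Group 1B, is unknown, because the documents give neither the share of partial forms nor the SD. The power figures above rest wholly on assumed values. The point is minor, but worth correcting because the endpoint is ranked in both testing schemes and the error would not show up in a range check.

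**What to change.** Replace the missing-item sentence in SAP Appendix F with: if at least 7 of the 13 items are answered, the total is computed by the formula above, that is, 13 x the mean of the answered item scores after reversal; otherwise the total is missing.

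This keeps the SAP's own formula, threshold and range, and settles the raw-or-reversed question. It costs one sentence and changes no design element, endpoint or test.
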